7.4.1. Pre-Titration Tolerability Assessment Requirements

Tolerability of investigational product must be assessed prior to titrating a patient to a higher dose. To determine if a patient is eligible for a dose up-titration refer to [Section 7.3](#).

7.5. Criteria for Study Termination

The Sponsor (Intercept Pharmaceuticals, Inc.) reserves the right to terminate the study at any time. It is normal procedure to review the emerging clinical and safety data. As a result of such a review or a recommendation by the Data Monitoring Committee (DMC), it may be necessary to stop the study before all patients have completed the study. In addition, the Sponsor may terminate the study at an investigational site at any time (eg, Good Clinical Practice [GCP] noncompliance or poorly performing sites, as determined by the number of patients enrolled or the quality of the study data).

The Investigator and/or Sponsor (or designee) must notify the Institutional Review Board/Independent Ethics Committee (IRB/IEC) of discontinuation of a site or the study and the reason for doing so.

Investigators will be informed by the Sponsor as to when the final study visit is to be completed, and should then schedule all patients for the end of study (EOS) or end of treatment (EOT) Visit.

8. SELECTION AND WITHDRAWAL OF PATIENTS

8.1. Patient Population

This study will be conducted at approximately 35 international study sites with experience in treating patients with PBC with moderate to severe hepatic impairment defined as CP-B and CP-C. Prospective patients will be identified primarily from the hospital and/or physician's database of patients with PBC, or may be referred from other physicians. Patients may self-refer to an Investigator if they become aware of the study through local, national, or international PBC patient societies, forums, or networks.

8.2. Patient Inclusion Criteria

1. A definite or probable diagnosis of PBC (consistent with American Association for the Study of Liver Diseases [AASLD] and European Association for the Study of the Liver [EASL] Practice Guidelines [[Lindor 2009](#), [EASL 2009](#)]), defined as having ≥ 2 of the following 3 diagnostic factors:
 - History of elevated ALP levels for at least 6 months
 - Positive antimitochondrial antibody (AMA) titer or if AMA negative or low titer ($\leq 1:80$), PBC-specific antibodies (anti-GP210 and/or anti-SP100) and/or

- antibodies against the major M2 components (PDC-E2, 2-oxo-glutaric acid dehydrogenase complex)
- Liver biopsy consistent with PBC (collected at any time prior to Screening)
2. Evidence of cirrhosis including at least one of the following:
 - Biopsy results consistent with PBC Stage 4
 - Liver stiffness as assessed by TE Median Value ≥ 16.9 kPa
 - Clinical evidence in the absence of acute liver failure consistent with cirrhosis including: gastroesophageal varices, ascites, radiological evidence of cirrhosis (nodular liver or enlargement of portal vein and splenomegaly)
 - Combined low platelet count ($< 140\,000/\text{mm}^3$) with
 - persistent decrease in serum albumin, or
 - elevation in prothrombin time /INR (not due to antithrombotic agent use), or
 - elevated bilirubin ($2 \times$ ULN)
 3. Satisfy the criteria of the modified CP classification for hepatic impairment during Screening (ie, within 14 days before the first dose of investigational product):
 - Moderate: CP-B (Scores 7 to 9) or
 - Severe: CP-C (Scores 10 to 12)
 4. MELD score of 6 to 24 at Screening
 5. Age ≥ 18 years
 6. Taking UDCA for at least 12 months (stable dose for ≥ 3 months) prior to Day 1, or unable to tolerate or unresponsive to UDCA (no UDCA for ≥ 3 months)
 7. Contraception: Female patients must be postmenopausal, surgically sterile, or if premenopausal (and not surgically sterile), be prepared to use ≥ 1 effective method of contraception during the study and for 30 days after the end of treatment visit. Effective methods of contraception are considered to be those listed below:
 - Barrier method, ie, (a) condom (male or female) with spermicide **or** (b) diaphragm with spermicide; or
 - Intrauterine device; or
 - Vasectomy (partner); or
 - Hormonal (eg, contraceptive pill, patch, intramuscular implant or injection); or
 - Abstinence, if in line with the preferred and usual lifestyle of the patient (where abstinence is defined as refraining from heterosexual intercourse)
 8. Must provide written informed consent and agree to comply with the study protocol.

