8.3. Patient Exclusion Criteria

1. Non-cirrhotic or cirrhotic CP-A (Mild; Score 5 to 6)
2. History of liver transplant or organ transplant
3. History of alcohol or drug abuse within 12 months prior to Screening
4. Hepatic encephalopathy (as defined by a West Haven score of ≥ 2 [AASLD, [EASL 2014](#)])
5. History or presence of other concomitant liver diseases including:
 - a. Hepatitis C virus infection and RNA positive
 - b. Active hepatitis B infection; however, patients who have seroconverted (hepatitis B surface antigen and hepatitis B e antigen negative) may be included in this study after consultation with the medical monitor
 - c. Primary sclerosing cholangitis
 - d. Alcoholic liver disease
 - e. Definite autoimmune liver disease or overlap hepatitis
 - f. Gilbert's Syndrome
6. In the opinion of the Investigator, fluctuating or rapidly deteriorating hepatic function prior to randomization
7. Patients with history or presence of hepatorenal or hepatopulmonary syndrome
8. Patients with significant active infection (ie spontaneous bacterial peritonitis)
9. Patients with known or suspected hepatocellular carcinoma
10. History of known or suspected clinically significant hypersensitivity to OCA or any of its components
11. Participation in another investigational product, biologic, or medical device study within 30 days prior to Screening. Participation in a previous study of OCA is allowed with 3 months washout prior to enrollment in this study
12. Mental instability or incompetence, such that the validity of informed consent or ability to be compliant with the study is uncertain
13. UDCA naïve (unless contraindicated)

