9.2.1. Drug Interactions

Bile acid sequestrants (BAS, including cholestyramine and its derivatives, colestipol, colesevelam, or other sequestrants) or aluminum hydroxide- or smectite-containing antacids should not be taken within 4 hours of taking investigational product (and UDCA if applicable), ie, BAS should be administered at minimum 4 hours before or 4 hours after investigational product administration.

OCA taken concomitantly with warfarin may result in decreased INR levels; therefore, INR should be monitored and the dosage of warfarin adjusted, as needed during treatment with OCA and after cessation of OCA, to maintain the target INR range.

The effect of OCA on drug metabolizing enzymes has been evaluated in both in vitro and clinical studies. The PK profile of caffeine, a sensitive CYP1A2 substrate probe, showed weak effect of OCA on CYP1A2. Based on these results, OCA may increase the exposure of narrow therapeutic index drugs that are substrates for CYP1A2, such as theophylline and tizanidine.

Information related to additional drug-drug interaction (DDI) studies is available in the current version of the IB. The aforementioned sections of the IB should be referred to during the course of the study, and are accessible to Investigators to help facilitate the assessment of potential DDIs with OCA that may be observed in study patients.

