14. EFFICACY ASSESSMENTS

14.1. Biochemical Measures of Disease Severity

14.1.1. Child-Pugh Score

Child-Pugh Score (Pugh 1973, Lucey 1997) is calculated and reported within the EDC system based on data entered into the eCRF by adding the scores from the 5 factors outlined in Table 10 and can range from 5-15. A total score of 5-6 is considered Grade A (mild, well-compensated disease); 7-9 is Grade B (moderate, significant functional compromise); and 10 and above is Grade C (severe, decompensated disease). Calculation of the CP Score includes Investigator assessments of ascites and hepatic encephalopathy, which may be assessed during the adverse event review at the scheduled visits, as well as total bilirubin, serum albumin, and prothrombin time, which will populate from the central laboratory. Investigators will be responsible for determining the appropriate dosing regimen based on the CP score (Table 1 and Table 10). Any change in CP Score will necessitate re-evaluation of the dosing regimen.

Table 10: Child-Pugh Scoring System

Factor	Units	Points		
		1	2	3
Serum bilirubin	mg/dL	<2.0	2.0-3.0	>3.0
Serum albumin	g/dL	>3.5	2.8-3.5	<2.8
Prothrombin time	Seconds prolonged	0-3	4-6	>6
	INR	<1.7	1.7-2.3	>2.3
Ascites		None	Mild	Moderate-Severe
Hepatic encephalopathy ^a		0	Grade 1 or 2	Grade 3 or 4

^a Grade 0: normal consciousness, personality, neurological examination, electroencephalogram
 Grade 1: restless, sleep disturbed, irritable/agitated, tremor, impaired handwriting, 5 cps waves
 Grade 2: lethargic, time-disoriented, inappropriate, asterixis, ataxia, slow triphasic waves
 Grade 3: somnolent, stuporous, place-disoriented, hyperactive reflexes, rigidity, slower waves
 Grade 4: unrousable coma, no personality/behavior, decerebrate, slow 2-3 cps delta activity
 (Pugh 1973, Lucey 1997)

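### An INR raised by an antithrombotic agent is discounted as evidence of cirrhosis but counted in the Child-Pugh entry score and stratum, so it can turn CP-A into CP-B and CP-B into CP-C

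*Protocol*

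**What the plan says.** All references are to Version 2 of the protocol.

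- **Cirrhosis (Section 8.2, inclusion 2; repeated in the Synopsis and Section 9.7.3).** A low platelet count supports cirrhosis if joined by one of three findings. One of these is "elevation in prothrombin time /INR (not due to antithrombotic agent use), or".
- **Child-Pugh entry (inclusion 3).** Patients must "Satisfy the criteria of the modified CP classification for hepatic impairment during Screening", with scores 7 to 9 (CP-B) or 10 to 12 (CP-C). No antithrombotic condition is attached.
- **MELD entry (inclusion 4).** "MELD score of 6 to 24 at Screening", also without condition.
- **Exclusion 1 (Section 8.3).** "Non-cirrhotic or cirrhotic CP-A (Mild; Score 5 to 6").
- **How the score is made.** Section 7.4 says the standard Child-Pugh calculation is used. Section 14.1.1 takes "total bilirubin, serum albumin, and prothrombin time, which will populate from the central laboratory", so no judgement is applied to the coagulation component.
- **Stratification (Section 9.4.1).** By CP class, B or C.
- **Concomitant drugs.** Section 9.2 leaves these to the care provider, Section 9.2.2 prohibits only commercial OCA, and Section 8.3 does not mention anticoagulants. Section 9.2.1 gives instructions for warfarin users: "OCA taken concomitantly with warfarin may result in decreased INR levels; therefore, INR should be monitored", and warfarin is adjusted to keep INR in its target range.
- **Endpoints (Sections 15.5 and 15.6).** Week 48 change in INR, Child-Pugh and MELD, and a clinical event of MELD 15 or more in patients with baseline MELD 12 or less.

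**The concern.** Inclusion 2 recognises that an INR raised by an antithrombotic agent says nothing about the liver. The next criterion in the same list then scores that INR as liver impairment. Followed as written, the rules admit cirrhotic CP-A patients whom exclusion 1 is meant to keep out, and they can place CP-B patients in the CP-C stratum.

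The primary objective is PK and safety in moderate to severe impairment, so the mix of patients is central to the trial. Eligibility and stratum are fixed at randomization, and no later analysis plan can undo them.

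A second, weaker strand concerns the endpoints. Where a patient takes warfarin, INR and the two scores built on it follow warfarin dosing as well as liver function.

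**Working it through.** The plan states no figure on this point, so there is none to reproduce. The check applies the protocol's own scoring rules and varies only INR.

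**Inputs**
- Table 10, Section 14.1.1: INR below 1.7 = 1 point, 1.7 to 2.3 = 2, above 2.3 = 3.
- Class limits, same section: "A total score of 5-6 is considered Grade A (mild, well-compensated disease); 7-9 is Grade B"; 10 and above is C.
- Section 14.1.2: MELD = 3.78 ln(bilirubin) + 11.2 ln(INR) + 9.57 ln(creatinine) + 6.43.
- Section 5.4.2: modelled total OCA plasma exposure 1.4-fold (CP-A), 8.0-fold (CP-B) and 13-fold (CP-C), relative to normal function.
- Sections 7.1 and 15.2: about 50 patients, 1:1, at least 20% CP-C.

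**1. Child-Pugh class.** Score = R + INR points, where R is the sum of the other four factors (minimum 4).

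| R | INR below 1.7 | INR 1.7 to 2.3 | INR above 2.3 |
|---|---|---|---|
| 4 | 5 (A) | 6 (A) | 7 (B) |
| 5 | 6 (A) | 7 (B) | 8 (B) |
| 6 | 7 (B) | 8 (B) | 9 (B) |
| 7 | 8 (B) | 9 (B) | 10 (C) |
| 8 | 9 (B) | 10 (C) | 11 (C) |

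A patient who scores 6 with a normal INR enters as CP-B at INR 1.7. One who scores 5 enters at INR above 2.3. A CP-B patient at 9 becomes CP-C at INR 1.7, and one at 8 at INR above 2.3.

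**2. What one patient weighs.** CP-B against CP-A modelled exposure: 8.0/1.4 = 5.7. At the 20% minimum there are 0.20 × 50 = 10 CP-C patients, about 5 per arm, so one misplaced patient is 1/5 = 20% of CP-C patients on OCA. One patient is 1/25 = 4% of an arm.

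**3. MELD entry.** With bilirubin and creatinine at 1 mg/dL, MELD is 6.43 at INR 1.0 and 6.43 + 11.2 ln(2.5) = 6.43 + 10.26 = 16.69 at INR 2.5. Both lie inside 6 to 24, so this patient's eligibility under inclusion 4 does not change.

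**4. Endpoints (assumed INR changes, liver unchanged).** Change in MELD = 11.2 ln(INR after / INR before).

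| INR | MELD change | Child-Pugh change |
|---|---|---|
| 2.5 to 2.2 | −1.43 | −1 |
| 2.5 to 2.0 | −2.50 | −1 |
| 3.0 to 2.0 | −4.54 | −1 |

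If 1 to 5 of 25 OCA patients take warfarin (assumed), the arm mean moves by between 1/25 × −1.43 = −0.06 and 5/25 × −4.54 = −0.91 MELD points, and by −0.04 to −0.20 Child-Pugh points.

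**5. MELD 15 or more.** From MELD 12 the event needs 3 points, an INR ratio of exp(3/11.2) = 1.31 on the unrounded formula. Starting an INR-raising agent on study could produce this. The patient in step 3 at INR 2.5 cannot have the event, because baseline MELD exceeds 12.

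**The case against.** The best case for the plan has five parts.

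- **Unmodified scores are a defensible choice.** Inclusion 2 diagnoses cirrhosis, and inclusion 3 applies a published score. That is fair, but it does not remove the conflict with exclusion 1: an anticoagulated cirrhotic patient whose liver scores 5 or 6 is admitted. The word modified in inclusion 3 does not help, since Section 7.4 specifies the standard calculation. Needing other evidence of cirrhosis does not help either, since cirrhotic CP-A is itself excluded.
- **Warfarin is adjusted to a target range.** This stands, and it matters. A reader might infer that the estimated effect on INR, MELD and Child-Pugh is biased in favour of OCA. The protocol does not support that: Section 9.2.1 says only that INR may fall, and it prescribes adjustment. The shifts in step 4 assume that adjustment has not restored INR. What remains is that an INR held at a target reflects warfarin dosing.
- **MELD entry.** A reader might infer that inclusion 4 also admits the wrong patients. Step 3 does not show this.
- **Adjudication.** Suspected liver-related events go to a blinded committee before analysis (Section 15.9), so it cannot be said that starting warfarin creates a counted event. Adjudication does not reach eligibility, stratum or the continuous endpoints.
- **Endpoint handling may be in the SAP.** It may, and the SAP is not at hand. There is also no formal hypothesis test, so no error rate is affected.

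**Conclusion.** The inconsistency between inclusion 2 on one side and inclusion 3 and the CP stratum on the other is real and should be corrected. It follows from the protocol's own table and needs no outside assumption: antithrombotic INR alone can add one or two Child-Pugh points, enough to cross either class boundary. For a CP-A patient counted as CP-B, the modelled exposure differs about 5.7-fold between the two classes.

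How many patients are affected is unknown. The protocol gives neither the number of anticoagulated patients nor the target INR range. With few users the effect on arm means is small; the greater exposure to error is in the small CP-C stratum.

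On the endpoints, the supportable statement is that changes in INR, MELD and Child-Pugh in warfarin users can reflect warfarin dosing rather than liver function. Adjustment to a target limits this without removing it. A demonstrated bias towards OCA, wrongful entry through MELD, or spurious counted MELD events would each go beyond the document.

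**What to change.** 1. **Entry and stratum.** Carry the inclusion 2 condition into inclusion 3 and Section 9.4.1: a patient on an antithrombotic agent must reach CP-B, or CP-C for that stratum, without PT/INR points attributable to that agent. State how attribution is decided.
2. **Endpoints.** Keep the standard Child-Pugh and MELD scores. Setting INR to 1.0 for anticoagulated patients would erase true hepatic coagulopathy. Add, if the SAP does not already have it, a sensitivity analysis of INR, MELD, Child-Pugh and the MELD 15 event that excludes or censors patients while on an agent that raises INR.
3. **Dose passages.** CP class also sets the maximum dose (Sections 7.3 and 7.4). The sponsor must reconcile those passages with the amended entry rule, so that a patient does not carry two conflicting classes. No dosing rule is proposed here.

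The cost is a clause in Section 8.2, one in Section 9.4.1, the reconciliation in item 3, and a flag from concomitant-medication data already collected under Section 9.2. The downside is that a few anticoagulated patients become ineligible, or are placed in the lower stratum when part of their INR rise is truly hepatic.

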8.3. Patient Exclusion Criteria

1. Non-cirrhotic or cirrhotic CP-A (Mild; Score 5 to 6)
2. History of liver transplant or organ transplant
3. History of alcohol or drug abuse within 12 months prior to Screening
4. Hepatic encephalopathy (as defined by a West Haven score of ≥ 2 [AASLD, [EASL 2014](#)])
5. History or presence of other concomitant liver diseases including:
 - a. Hepatitis C virus infection and RNA positive
 - b. Active hepatitis B infection; however, patients who have seroconverted (hepatitis B surface antigen and hepatitis B e antigen negative) may be included in this study after consultation with the medical monitor
 - c. Primary sclerosing cholangitis
 - d. Alcoholic liver disease
 - e. Definite autoimmune liver disease or overlap hepatitis
 - f. Gilbert's Syndrome
6. In the opinion of the Investigator, fluctuating or rapidly deteriorating hepatic function prior to randomization
7. Patients with history or presence of hepatorenal or hepatopulmonary syndrome
8. Patients with significant active infection (ie spontaneous bacterial peritonitis)
9. Patients with known or suspected hepatocellular carcinoma
10. History of known or suspected clinically significant hypersensitivity to OCA or any of its components
11. Participation in another investigational product, biologic, or medical device study within 30 days prior to Screening. Participation in a previous study of OCA is allowed with 3 months washout prior to enrollment in this study
12. Mental instability or incompetence, such that the validity of informed consent or ability to be compliant with the study is uncertain
13. UDCA naïve (unless contraindicated)

8.4. Dose Adjustment, Interruption, and Withdrawal from Investigational Product or Study

Investigational product may be temporarily decreased (eg, by decreasing dosing frequency) or temporarily or permanently stopped based on tolerability concerns. The dose of investigational product should be resumed to the maintenance dose in a blinded manner once the issues relating to the lack of tolerability are resolved.

Patients who are discontinued from investigational product prior to completion of the study are encouraged to continue to follow the regular visit schedule, with the exception of PK sampling, but may withdraw consent at any time.

8.4.1. Reasons for Additional Monitoring or Mandatory Interruption of Investigational Product

8.4.1.1. Reasons for Additional Monitoring Related to Liver Chemistries

Patients who develop ALT or AST $>2\times$ baseline (and $>ULN$) or total bilirubin $>1.5\times$ baseline (and $>ULN$) should have repeat testing within 48 to 72 hours to confirm values. Patients with persistent elevations (eg, additional lab testing per Investigator discretion) should be closely monitored. Concomitant elevations in total bilirubin or INR with persistent increases in ALT or AST should also be closely monitored.

8.4.1.2. Reasons for Investigational Product Interruption Related to Elevated Liver Chemistries

Development of any of the following clinical laboratory values, without explanation, during the study mandates investigational product interruption:

- AST and/or ALT $>3\times$ baseline (and $>ULN$)
- Total bilirubin $>2\times$ baseline (and $>ULN$)

Repeat testing within 48 to 72 hours to confirm the abnormalities and to determine if they are increasing or decreasing should be performed. Detailed adverse event information should also be collected, and the patient should be investigated for possible causes of the liver chemistry changes, as appropriate. The Investigator should obtain a history of concomitant medications (including nonprescription medications and herbal and dietary supplement preparations) and other possible causes of liver enzyme and bilirubin increases. Any potentially hepatotoxic medications should be identified and discontinued if advisable.

If symptoms persist or repeat testing shows AST or ALT $>3\times$ baseline (and $>ULN$) or total bilirubin $>2\times$ baseline (and $>ULN$), patients should be followed as clinically indicated depending on other laboratory and clinical signs and symptoms.

For the purposes of this protocol, if the above referenced significant elevation in liver enzyme or bilirubin levels resolve following interruption of investigational product and no other cause for the elevation is identified, the elevations should be assumed to be related to investigational product and investigational product should be discontinued. If the liver enzyme or bilirubin levels do not resolve following interruption of investigational product and no other cause for the elevation is identified, it may be assumed that the elevations were due to disease progression and the patient may be re-challenged following a discussion between the Investigator or designee and the Sponsor.

Elevation of liver enzymes or bilirubin is based on comparison to baseline values defined as the mean of all available Screening and Day 1 values, which are the mean of all available evaluations prior to the first administration of investigational product. At least 2 of these samples will be obtained a minimum of 2 weeks apart during the Screening period. Elevations that occur gradually over the course of the study may be indicative of disease progression and should be assessed as clinically appropriate. Liver enzyme and bilirubin elevations that occur over a shorter time, such as within a 6-month period, should be evaluated for drug-induced liver injury as provided in the guidelines below.

If at any time a patient develops signs or symptoms of hepatotoxicity such as new onset fatigue, nausea, vomiting, right upper quadrant pain or tenderness, fever, rash, and/or eosinophilia (>7%) in combination with elevations in liver enzymes, investigational product should be interrupted and liver enzymes monitored until signs or symptoms resolve.

Patients who develop evidence of severe drug-induced liver injury that is suspected to be causally related to the investigational product should be discontinued from investigational product and should not be rechallenged. Severe drug-induced liver injury includes, but is not limited to, functional hepatic impairment, as indicated by rising bilirubin or INR that cannot be explained by progression of disease. Natural progression of the underlying condition and other causal factors such as a common bile duct stone or development of other concurrent liver disease should be considered before the investigational product is permanently discontinued.

If after all investigations and actions outlined above have been completed, the investigator determines that the elevations in liver biochemistries are considered not related to investigational product, the Sponsor must be contacted before investigational product can be reinitiated. Follow-up procedures for patients resuming treatment, including laboratory evaluations and physical examinations, must be performed after a maximum of 2 weeks of retreatment. Results must be reported to the site as soon as possible so the Investigator can determine if it is appropriate for the patient to continue treatment.

The Medical Monitor must be contacted in all cases of persistent liver biochemistry elevations.

All hepatic injury events, regardless of relationship to investigational product, will be adjudicated by the Hepatic Safety Committee (see [Section 15.9](#)).

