13.1.8. Follow-Up of AEs and SAEs

All AEs must be followed during the course of the study until the AE resolves, is no longer of clinical concern, has stabilized or is otherwise explained, or the patient is lost to follow-up.

AEs ongoing at the final visit that are deemed to be “possibly, probably, or definitely” related or of other clinical significance must be followed for as long as necessary to adequately evaluate the safety of the patient or until the event stabilizes, resolves, or is no longer of clinical concern. If resolved, a resolution date for the AE should be documented on the eCRF. The Investigator must ensure that follow-up includes any supplemental investigations indicated to elucidate the nature and/or causality of the AE. This may include additional laboratory tests or investigations, or consultation with other healthcare professionals, as considered clinically appropriate by the Investigator.

All patients showing possible drug-induced liver injury should be followed until all abnormalities return to normal or to the baseline state. Drug-induced liver injury may develop or progress even after the causative drug has been stopped. Results should be recorded in the eCRF. Note that longer follow-up can sometimes reveal an off-drug repetition of what had appeared to be drug-induced liver injury, indicating that liver injury was related to underlying liver disease.

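### Section 8.4.1.2 lets failure of liver values to resolve off product stand as grounds for assuming disease progression and re-challenging, although Section 13.1.8 says drug-induced liver injury can progress after the drug is stopped

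*Protocol*

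**What the plan says.** The text at issue is in Version 2 of the protocol (22 May 2017). Section 8.4.1.2 makes interruption mandatory when ALT and/or AST exceeds 3x baseline, or total bilirubin exceeds 2x baseline (each also above ULN), without explanation. It then asks for an early repeat: "Repeat testing within 48 to 72 hours to confirm the abnormalities and to determine if they are increasing or decreasing should be performed". After that it gives two branches, both for the case where no other cause is found.

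- Values resolve off product: "the elevations should be assumed to be related to investigational product and investigational product should be discontinued".
- Values do not resolve off product: "it may be assumed that the elevations were due to disease progression and the patient may be re-challenged following a discussion" with the Sponsor.

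Later in the same section, patients with severe drug-induced liver injury suspected to be caused by the product "should be discontinued from investigational product and should not be rechallenged". The description of severe injury includes a rise in bilirubin or INR for which disease progression offers no explanation. Product may be restarted once the investigations are complete and "the investigator determines that the elevations in liver biochemistries are considered not related to investigational product"; in that case "the Sponsor must be contacted before investigational product can be reinitiated".

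Section 13.1.8 says of possible drug-induced liver injury that patients "should be followed until all abnormalities return to normal or to the baseline state", and adds: "Drug-induced liver injury may develop or progress even after the causative drug has been stopped".

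**The concern.** The second branch draws a causal conclusion from persistence off drug. That conclusion would be sound only if drug injury could be expected to improve once the drug is withdrawn. Section 13.1.8 says it need not. A patient whose liver injury continues after the drug is stopped looks, on this criterion, the same as a patient whose disease is progressing, and the rule allows both to be treated as progression.

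The outcome is also lopsided. An unexplained elevation that settles off drug leads to discontinuation, while one that does not settle may lead to re-exposure. The population has Child-Pugh B or C disease. Section 5.5 associates hepatotoxicity with increased liver concentrations of OCA, and Section 5.4.2 reports model predictions of liver concentrations 1.5-fold (Child-Pugh B) and 1.7-fold (Child-Pugh C) those with normal hepatic function. Safety is a primary objective, and a re-challenge rule belongs in the protocol rather than in an analysis plan.

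**Working it through.** There is no figure to reproduce, because the point concerns a decision rule. The check sets the two sections side by side and then asks of each safeguard whether it makes anything beyond non-resolution a condition of re-challenge.

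**The inference.** Section 8.4.1.2 needs two facts: the values have not resolved, and no other cause has been identified. From these it permits progression to be assumed. Section 13.1.8 says drug injury may progress off drug, so the first fact is compatible with drug injury. The second rules out third causes but does not decide between drug and disease. Neither fact is evidence for progression over drug injury.

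**The safeguards**, all in 8.4.1.2 unless noted:

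- *Repeat test at 48 to 72 hours* (2 to 3 days). It is meant to show direction, but its result is not made a condition of re-challenge.
- *Work-up of causes and review of concomitant medication.* This addresses other causes. The rule at issue starts where that work-up finds none.
- *Evaluation for drug injury when the rise occurs over a shorter time, such as 6 months.* This is a real check, but the assumption of progression is not limited to gradual rises.
- *Interruption and monitoring when symptoms accompany enzyme elevations.* This does not reach a patient without symptoms.
- *Severe-injury bar on re-challenge.* Its bilirubin/INR indicator applies only where progression does not explain the rise. The text does not say whether progression assumed from non-resolution alone counts as an explanation. If it does, the assumption can lift the bar.
- *Investigator determination that the elevation is unrelated, made after the investigations.* This is required, but nothing prevents it from resting on the same assumption.
- *Contact with the Sponsor before restart, and with the Medical Monitor in every persistent case.* Both are mandatory. Neither carries criteria for allowing re-challenge.
- *Laboratory tests and examination within 2 weeks of retreatment.* These come after re-exposure.
- *Hepatic Safety Committee adjudication* (8.4.1.2 and 15.9). It is required before events enter an analysis and is not a gate on restarting product.

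**Result.** The safeguards put informed people in the decision and give them information. None expressly requires evidence of progression other than non-resolution, and 8.4.1.2 states no off-drug observation period before the assumption may be made.

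**The case against.** The strongest reply has four parts.

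First, the rule is permissive, and both sections state possibilities, so they do not flatly contradict each other. That is correct. The fault is that one section permits an inference which the other shows to be unsupported.

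Second, a reader might infer that nothing stops re-challenge of a patient whose values are still rising. The documents do not support that. The severe-injury rule, the drug-injury evaluation of shorter-onset rises, the unrelatedness determination after investigation, the Sponsor discussion and the Medical Monitor contact all stand in the way, and the more natural reading is that the determination follows a real work-up. What remains is narrower: no written criterion requires evidence beyond non-resolution.

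Third, the protocol does treat the off-drug course as informative. Table 7 uses improvement on stopping as evidence of relatedness, and Section 13.1.8 adds that longer follow-up can reveal an off-drug recurrence pointing to underlying disease. This stands, but it argues for watching longer before attributing cause. A recurrence off drug is positive evidence; mere persistence is not.

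Fourth, an absolute demand for stable or falling values would keep true progressors off product while they worsen, and would bind placebo patients under the blind, whose elevations cannot be OCA injury. This is a fair trade-off, and the fix below allows for it. A fixed off-drug interval is likewise optional: the 2-week spacing in 8.4.1.2 serves to establish a baseline and is a weak precedent for observing injury. Section 13.1.8 already calls for follow-up to normal or baseline, and the DMC reviews laboratory data about quarterly, so such patients would not go unobserved.

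Appendix A records that this section was added to meet post-marketing requirements. That shows the section was deliberate; it does not show that this particular inference was endorsed.

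**Conclusion.** The point holds and should be fixed. Section 8.4.1.2 permits progression to be assumed from non-resolution with no other cause found, an inference that Section 13.1.8 undercuts, and the assumption can carry over into the severe-injury bar on re-challenge. It concerns asymptomatic or otherwise non-severe, persistent, unexplained elevation after mandatory interruption.

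Its size is not quantified. The documents give neither the rate of such elevations nor the rate at which drug injury progresses off drug, so no frequency of harm is claimed, and no sample size or error rate depends on the rule. The conclusion rests on reading the two sections as written and on the absence of any stated evidential condition for the assumption. Careful use of the existing discussions could avoid the problem in practice, but the text does not require it.

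**What to change.** In Section 8.4.1.2, state that:

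1. non-resolution off product does not by itself establish disease progression or unrelatedness to product;
2. progression assumed only from non-resolution does not count as an explanation of rising bilirubin or INR under the severe-injury rule against re-challenge;
3. the off-drug trend in bilirubin, ALT/AST and INR must be reviewed and documented in a discussion between Investigator, Sponsor and Medical Monitor before any re-challenge, with no re-challenge while bilirubin or INR is still rising unless evidence other than non-resolution supports progression.

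Keep the present safeguards, and keep the discontinuation rule for elevations that resolve off drug. A fixed observation interval, for example two off-drug results at least 2 weeks apart, may be added but is not essential.

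The cost is a wording change in one section. The off-drug tests fall within the follow-up that Section 13.1.8 already asks for in possible drug-induced injury. The downside is that some patients with true progression may resume product later.
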